5.3 LIFESTYLE CONSIDERATIONS

Not applicable

5.4 SCREEN FAILURES

Screen failures are defined as participants who consent to participate in the clinical trial but are not subsequently randomly assigned to the study intervention or entered in the study. A minimal

set of screen failure information is required to ensure transparent reporting of screen failure participants, to meet the Consolidated Standards of Reporting Trials (CONSORT) publishing requirements and to respond to queries from regulatory authorities. Minimal information includes demography, screen failure details, eligibility criteria, and any serious adverse event (SAE).

5.5 STRATEGIES FOR RECRUITMENT AND RETENTION

Recruitment:

The target sample for this study will include patients between the ages of 14 and 21, who had a primary ACL reconstruction by one of the referring physicians. Participants will be excluded if they have a history of more than one ACL reconstruction, post-operative complications that required additional surgical intervention, hospitalization for any reason other than the ACL reconstruction in the last 3 months, plans for additional surgical procedures in the next 12 months, or any other health conditions determined by the study team to be contraindications to participating in the biofeedback program. Patients will also be excluded if they live greater than 60 miles from the research lab or have limitations that would prevent them from attending the biofeedback training sessions. In order to meet inclusion criteria and be enrolled in the study, participants need to have undergone a primary ACL reconstruction, completed post-operative physical therapy and be released by his/her treating orthopaedic surgeon to return to full sport participation.

Based on our prior and ongoing studies, we are confident that 40 participants can be enrolled within the 24 month recruitment period. We will use the electronic medical record to identify all patients who had an ACL reconstruction within the last 4 months or who are scheduled to have an ACL reconstruction with any of the referring orthopaedic surgeons. The medical records will be used to determine eligibility based on study inclusion and exclusion criteria. The parents, if the patient is a minor, of all potentially eligible patients will be approached by the treating orthopaedic surgeon or member of the surgeon's clinical staff. If the patient is over the age of 18, he/she will be approached directly by the treating orthopaedic surgeon. The three referring physicians have been working with the research study team on the recruitment and enrollment of ACL reconstruction patients for the last 4 months on an industry sponsored knee brace study. During this time the study team has been able to implement a successful recruitment procedure in which the patients are identified by the physician extenders in each clinic. These individuals then discuss the research study with the potential subject to determine the subject's interest in participation.

Retention:

All participants will be treated with respect, and we will be considerate of the time and energy that is involved with participation in this study. Participant retention will begin with the recruitment process. Based on medical records and release of information consent forms from the treating physician, only those patients who do not actively opt out will be contacted by phone to receive follow-up information about the study and assess their interest in participating. Once enrolled in the study, all participants will have contact with the study team at each measurement time point (baseline, 6 weeks and 12 weeks). In addition, based on group randomization the participants will also have contact with the study team either two times a week for six weeks or once a week for six weeks. Based on our prior experience, this level of contact helps to keep participants engaged. Calls to participants will also be scheduled at times that are preferred and convenient for each participant. We will also use telephone calls to remind participants about all in-person study visits. Participants not assigned to patient intervention arm will be

asked to complete 3 in-person educational sessions as well as three online training modules over the 6 week intervention period. This will encourage continued participation from patients assigned to this arm. Also, the importance of compliance will be emphasized throughout the study. Participants who do decide to withdraw from study participation however, will be encouraged to complete the study assessments. The reason for any missed intervention sessions as well as assessment sessions will be recorded for future analysis in order to improve planning for subsequent clinical trials.

All successful and unsuccessful attempts to contact participants will be documented within the subjects study record. Additionally, alternate contact numbers will be requested from participants to aide in locating the subject.

Participant recruitment and retention statistics will be collected and monitored on a regular basis such that any problems or negative trends can be identified early and appropriate measures taken and/or procedures modified.

6 STUDY INTERVENTION

6.1 STUDY INTERVENTION(S) ADMINISTRATION

6.1.1 STUDY INTERVENTION DESCRIPTION

This will be a randomized controlled Phase 1, pilot clinical trial. Patients will be assigned to one of two study arms: 1) Biofeedback Intervention, 2) Attention Control. All participants in the study will continue with any other usual medical care they receive for their ACL reconstruction.

BIOFEEDBACK INTERVENTION

The 6-week biofeedback training program is focused on altering loading and movement asymmetry during biweekly sessions on non-consecutive days (12 sessions). The biofeedback training program will provide sensory (visual and tactile) feedback to the subject to heighten awareness of asymmetrical movement strategies (e.g. load shift, movement asymmetry) during a squat. The two exercises that will be completed during the biofeedback training program will be a visual feedback squat and a resisted squat (tactile feedback). Each of these tasks will be completed 30 (3 sets of 10 repetitions) times per session. We will provide a 20 second rest between trials, and a 10 minute break between the visual and tactile feedback exercises to decrease the effect of fatigue. Prior to the biofeedback intervention session, each participant will complete a 5-minute warmup on a stationary bike as was described during the biomechanical assessments.

Visual feedback: The simplest way to provide biofeedback during a squat is through visual feedback of load. Under this approach, subjects are asked to stand on force plates, which measure the ground reaction forces (load) beneath each foot. Shoulder width for each participant will be measured as the distance between acromioclavicular joints. This distance will then be measured on the force plates and 2 pieces of tape will be placed this distance apart (one on each force plate) and participants will be asked to stand with one heel on each piece of tape. Stance width will be recorded on the data collection sheet and then entered into REDCap so that this distance can be used during each subsequent training and testing session and foot position can be measured and marked prior to participant arrival. Participants face a projection screen that displays two bar graphs of the vertical ground reaction force, depicting each foot's

load. Subjects will be asked to stand with their feet shoulder width apart (one foot on each force plate) with their hands in front on them with the shoulder flexed to 90 degrees for counter weight. The foot width will be standardized to ensure that foot placement is consistent for both the squatting trials as well as during the biofeedback training. The subject will be asked to squat down until their thighs are parallel with the ground or until their heels begin to come off from the ground, whichever occurs first. A stool will be placed behind the subject and will be set to the height where the subject's thigh will be parallel to the ground if they sat down (stool will be placed at the height of the popliteal fold), so that the subject will know the deepest position they have to achieve. If the subject is able to achieve a squat position where the thigh is parallel to the floor they will be instructed to squat until they barely touch down on the bench and then slowly stand back up without transferring any weight to the bench. Subjects are asked to squat down and watch the change in load beneath each foot. After completing the first squat, subjects will be asked to complete all subsequent squats with the goal of keeping the bars level on the graph or maintaining equal within a $LSI \geq 90\%$ (symmetric) load on both feet. This process will be completed a total of 30 times (3 sets of 10 repetitions each) during each of the training sessions with the same goal each time of maintaining the bars at an equal level. This is a simple measure that subject can easily understand and that can be altered through biofeedback.²⁴

Tactile feedback: The second set of exercises at each biofeedback session will be resisted squats. A subject will be asked to squat while an external force is applied to the side of the knee (Figure 3) requiring the subject to work against this resistance to maintain balance and complete the squat. The band will be placed on the surgical limb of each patient and will be pulled at approximately a 45 degree angle toward the contralateral side. Pulling the subject toward the non-operative limb (one that is typically displaying higher loads) will require the subject to pull toward the surgical limb and maintain good frontal plane position by resisting frontal plane valgus. This is a typical exercise utilized in the clinic to aid in equal weight bearing and active hip abduction. The squat position that will be used during these exercises will be the same as the squat position used in both the visual biofeedback task as well as during the biomechanical testing. The subjects will be asked to stand with their feet at the standardized width and again squat until they make contact with the stool that will be positioned behind them during the biofeedback session. Subjects will be asked to complete 30 tactile feedback squats (3 sets of 10 squats) during each of the biofeedback sessions.

ATTENTION CONTROL

The 6-week attention control group program will focus on providing educational information to the participants related to the clinical and sports expectations as they are released to return to sport. These participants will be asked to meet 6 times during the 6-week intervention time period. Three of these visits will be completed in person and three will be completed using an online educational module (6 sessions). The online sessions will be completed in week 1, week 3, and week 5 while the in person sessions will be completed during week 2, week 4, and week 6. The content of these sessions will focus on providing information on ACL reconstruction, athlete expectation as they return to sport, incidence and risk factors for secondary ACL injuries, as well as some suggestions on the gradual progression back into sport.

6.1.2 DOSING AND ADMINISTRATION

The dose for each participant will be dependent on the group to which he/she is randomized. However, the dose will be the same for all participants in the Biofeedback Intervention as well as being the same between all participants in the Attention Control arm of the study.

BIOFEEDBACK INTERVENTION

The 6-week biofeedback training program is focused on altering loading and movement asymmetry during biweekly sessions on non-consecutive days (12 sessions). The biofeedback training program will provide sensory (visual and tactile) feedback to the subject to heighten awareness of asymmetrical movement strategies (e.g. load shift, movement asymmetry) during a squat. The two exercises that will be completed during the biofeedback training program will be a visual feedback squat and a resisted squat (tactile feedback). Each of these tasks will be completed 30 (3 sets of 10 repetitions) times per session. We will provide a 20 second rest between trials, and a 10 minute break between the visual and tactile feedback exercises to decrease the effect of fatigue.

ATTENTION CONTROL

The 6-week attention control group program will focus on providing educational information to the participants related to the clinical and sports expectations as they are released to return to sport. These participants will be asked to meet 6 times during the 6-week intervention time period. Three of these visits will be completed in person and three will be completed using an online educational module (6 sessions). The online sessions will be completed in week 1, week 3, and week 5 while the in person sessions will be completed during week 2, week 4, and week 6. The content of these sessions will focus on providing information on ACL reconstruction, athlete expectation as they return to sport, incidence and risk factors for secondary ACL injuries, as well as some suggestions on the gradual progression back into sport.

6.2 PREPARATION/HANDLING/STORAGE/ACCOUNTABILITY

6.2.1 ACQUISITION AND ACCOUNTABILITY

Not applicable

6.2.2 FORMULATION, APPEARANCE, PACKAGING, AND LABELING

Not applicable

6.2.3 PRODUCT STORAGE AND STABILITY

Not applicable

[figure not shown]
6.2.4 PREPARATION

Not applicable

6.3 MEASURES TO MINIMIZE BIAS: RANDOMIZATION AND BLINDING

This will be a randomized controlled trial (see figure below).

Participating patients will be randomized using a 1:1 between the Intervention vs. Control arms.

Participants will be equally allocated between the two groups, with randomization stratified according to gender, age and activity level to ensure that the groups are balanced in these respects. All participants in the study will continue with any other usual medical care they receive for their ACL reconstruction.

Eligible participants will be randomized following the first biomechanical assessment (during which informed consent is obtained). After this baseline biomechanical assessment, participants will be scheduled for his/her first study visit (biofeedback intervention or control in-person education session) at this time each participant will be informed about the research arm to which they have been assigned. The Research Assistant will call participants within 24-48 hours of each appointment to remind them of their appointment day and time as well as answer any questions.

Randomization will be based on a computer generated sequence maintained by the project statistician. The Research Assistant or Principle Investigator will obtain the randomization status from the statistician.

Participant randomization assignments will be entered and stored in a password protected, study specific database maintained by the research assistant and verified by the study statistician.

As this is an open trial, therefore, participant unblinding procedures are not necessary.

6.4 STUDY INTERVENTION COMPLIANCE

All members of the study staff will endeavor to maximize adherence to the study's protocol and minimize non-compliance. However, it is the responsibility of the Principal Investigator to report all protocol deviations/violations to the Virginia Tech IRB within 10 business days of the time the PI becomes aware to the event. In addition, the PI will include a summary of any protocol deviations/violations in the biannual report to the study's Safety Officer. Protocol deviations will be collected, analyzed, and monitored in the study's protocol deviation log, which is kept in the Investigator's regulatory files within a locked file cabinet. A sample protocol deviation form can be found in the MOOP (Appendix J).

Protocol deviations include, but are not limited to, the following examples:

- Enrollment or randomization of an ineligible participant
- Follow-up visit at a time point different from that specified in the protocol
- Failure to obtain Informed Consent
- Entering a participant into another clinical study

- Failure to keep IRB approval up-to-date
- Wrong treatment administered to participant

6.5 CONCOMITANT THERAPY

Not applicable

6.5.1 RESCUE MEDICINE

Not applicable

7 STUDY INTERVENTION DISCONTINUATION AND PARTICIPANT DISCONTINUATION/WITHDRAWAL

7.1 DISCONTINUATION OF STUDY INTERVENTION

Discontinuation from the ACL Biofeedback intervention does not mean discontinuation from the ACL Biofeedback Pilot study, and remaining study procedures should be completed as indicated by the study protocol. If a clinically significant finding is identified (including, but not limited to changes from baseline) after enrollment, the investigator or qualified designee will determine if any change in participant management is needed. Any new clinically relevant finding will be reported as an adverse event (AE).

The data to be collected at the time of study intervention discontinuation will include the following:

- At the time of discontinuation an AE or SAE report will be completed and submitted to the IRB as well as to KAI per the information included in the MOOP (Section 10.0 Safety Reporting).

7.2 PARTICIPANT DISCONTINUATION/WITHDRAWAL FROM THE STUDY

Participants are free to withdraw from participation in the study at any time upon request. An investigator may discontinue or withdraw a participant from the study for the following reasons:

- Pregnancy
- Significant study intervention non-compliance
- If any clinical adverse event (AE), or other medical condition or situation occurs such that continued participation in the study would not be in the best interest of the participant
- If the participant meets an exclusion criterion (either newly developed or not previously recognized) that precludes further study participation
- Study participant sustains an ACL tear of either limb
- Participant unable to attend the ACL Biofeedback intervention session for 2 days/weeks

The reason for participant discontinuation or withdrawal from the study will be recorded on the Case Report Form (CRF) (MOOP Appendix K). Subjects who sign the informed consent form

and are randomized but do not receive the study intervention may be replaced. Subjects who sign the informed consent form, and are randomized and receive the study intervention, and subsequently withdraw, or are withdrawn or discontinued from the study, will be replaced.

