4.1 OVERALL DESIGN

Aim 1: Determine the impact of a biofeedback training program on decreasing asymmetrical vertical ground reaction forces, frontal plane knee range of motion and the peak knee extension moment, known risk factors for secondary ACL injuries.
We will test the hypothesis that our biofeedback program will decrease the risk of secondary ACL injury by improving loading and movement symmetry during the dynamic task of landing from a jump 6 weeks post intervention.

Aim 2: To demonstrate our ability to recruit, retain and determine patient compliance in completing a biofeedback retraining program. We will demonstrate our ability to recruit 40 ACL reconstructed patients and assess study retention and compliance.

Overview: The goal of this single site, pilot randomized clinical trial is to determine the impact of an innovative biofeedback training program on decreasing surrogate measures of secondary ACL injury risk in adolescent athletes. Movement and loading symmetry will be assessed using the limb symmetry index ($LSI = \frac{ABS[Surgical] - ABS[Nonsurgical]}{0.5(ABS[Surgical] + ABS[Nonsurgical])} * 100$)^{2,3,7,34} prior to (baseline) and at two time points following (immediately following training (efficacy), and 6 weeks after (durability)) the biofeedback training program (**Aim 1; Figure 1**).

40 adolescent ACL patients (20 control, 20 intervention) will be recruited. Subjects will be block randomized into either the control arm or the intervention arm at baseline. All intervention subjects will complete an in-person (no home exercises) biofeedback retraining program for 6 weeks (2 times per week) with a focus on improving both load and movement symmetry through the use of tactile and visual feedback (**Figure 1**), which has been reported to be an effective biofeedback intervention²⁶. Finally, this study will demonstrate our ability to recruit subjects, engage them in the novel biofeedback program, and retain them until study completion. The outcomes from **Aim 2** will inform future study designs.

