sponsored knee brace study. During this time the study team has been able to implement a successful recruitment procedure in which the patients are identified by the physician extenders or the surgeon and the above described procedure has been completed in each clinic. If a patient is interested in participating, the signed consent to release information is sent to the research study team and the secondary medical record screening is completed. Informed consent and assent will be approved by the institutional review board.

Prior to the start of the study, all participants (and parents will complete parental permission and patient will complete ascent if participant is <18 years old) will complete informed consent in person in the lab. The consent form will be sent to the potential participant by email or mail based on the patient's preference prior to study enrollment. Potential participants (parents if the potential participant is a minor) will be allowed to review the consent form prior to his/her first visit to the lab. Each participant will be allowed ample time to review the consent form and determine if he/she is interested in participating in the study. All questions will be answered prior to the consent form being signed and the study being initiated. If a consented subject becomes 18 during the course of the study he/she will be consented as an adult at the next study visit.

Following administration of the consent and HIPAA authorization, we will measure height and weight and determine BMI. If female participants become pregnant, their active involvement in the study will end because later stage pregnancy will alter movement mechanics due to increased joint laxity. In addition, weight gain would also likely confound study results. As part of the telephone screening process, women will be excluded if they self-report being pregnant or planning to become pregnant.

We will aim to ensure that subject selection is equitable and all relevant demographic groups have access to study participation by contacting all patients who meet inclusion / exclusion criteria, regardless of demographic characteristics. We have also aimed to produce recruitment and intervention materials that are appropriate for individuals with low literacy or education levels. We will continue to recruit patients until we reach our sample size goal of n=40.

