9.2 SAMPLE SIZE DETERMINATION

This is a pilot study, with the purpose of discerning parameter estimates for use in powering a subsequent multi-center clinical trial. To estimate statistical power for this pilot design, we consider a comparison of outcomes by group across time. Previous studies have not examined the knee extension moment limb symmetry index, therefore the difference in knee joint position and the knee extension moment will be employed as proxy variables in order to estimate statistical power for this pilot design. We considered a comparison of outcomes between pre- and post-intervention^{17,18} and side-to-side differences in ACL-R patients. (Table 4).¹⁵

Using 2-sided testing between groups based on previous results, we will need 14 patients overall randomized at 1:1 ratio assuming 80% power to detect a significant difference in the knee extension moment between the groups with $\alpha=0.05$.¹³ Therefore, with recruitment of 40 subjects (goal of retaining 30

Table 4: Sample Size Calculations (N=sample size per group)

	Pre-intervention	Post-intervention	Sample Size
Peak Knee Extension Moment ¹⁰	3.7 ± 0.9	2.4 ± 0.5	N=7
Peak Knee Flexion ¹⁸	88.8 ± 8.0	105.0 ± 5.6	N=5
	Control	Intervention	Sample
Knee Flexion Angle ¹⁸	83.5 ± 20.5	103.8 ± 16.3	N=15
Vertical ground reaction force ¹⁸	2.0 ± 0.4	1.6 ± 0.3	N=14

subjects through study completion), we are adequately powered to declare significance. Thus, while not the primary purpose of this experiment, we are adequately powered to declare significance between groups.

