9.4.3 ANALYSIS OF THE SECONDARY ENDPOINT(S)

For **Aim 2**, we will calculate rates of recruitment, retention and compliance. No hypothesis tests will be performed. However, correlates to these metrics will be assessed. For each of the outcome measures the between session analysis will allow us to calculate test-retest reliability. The use of correlations will allow us to compute criterion and predictive validity.

Study retention will be defined as a subject who attends each of the biomechanical testing session (baseline, immediately following intervention (intervention)/6 weeks after baseline (control), and then 6 weeks after training (intervention) or 12 week after the baseline (control). Proportion retention will be computed by dividing the number of retained subjects at the end of the intervention by the total number of patients randomized into the study. Compliance with the intervention will be defined as a subject who attends at least 80% of the biofeedback training sessions during the six weeks of the intervention. Proportion adherence will be computed by dividing the number of sessions attended by the total number training sessions (number of training sessions n=12).

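### Section 7.2 requires replacement of participants who withdraw after receiving the intervention, which is not reconciled with a plan for 40 that already allows for 10 losses

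*Combined protocol and SAP*

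**What the plan says.** **Replacement (section 7.2).** There are two rules. For people who consent "and are randomized but do not receive the study intervention may be replaced", replacement is optional. For those randomised who "receive the study intervention, and subsequently withdraw, or are withdrawn or discontinued from the study, will be replaced", it is mandatory.

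**Grounds for withdrawal (section 7.2).** The list just above these rules gives reasons for which the investigator may withdraw someone. It includes "Significant study intervention non-compliance", adverse events and "Study participant sustains an ACL tear of either limb". It also includes being unable to attend the biofeedback sessions for a stated period, which on its wording can apply only in the biofeedback arm.

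**Planned size.** Section 4.1: "40 adolescent ACL patients (20 control, 20 intervention) will be recruited". Section 8.1: "We will continue to recruit patients until we reach our sample size goal of n=40". Section 9.2 links size to attrition: "with recruitment of 40 subjects (goal of retaining 30" through to study completion.

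**Retention (section 9.4.3).** The proportion is obtained by "dividing the number of retained subjects at the end of the intervention by the total number of patients randomized into the study".

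**Analysis set (section 9.3).** The modified ITT set requires attendance at half or more of the biofeedback-arm visits and at least one assessment after the intervention.

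**Not stated anywhere.** The documents give no maximum number randomised, no rule for placing a replacement in the sequence described in section 6.3, and no statement on whether a replaced participant stays in the analysis.

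**The concern.** A trial can allow for attrition by over-recruiting or by replacing losses. Section 9.2 does the first and section 7.2 requires the second, so the plan as written provides for the same losses twice and leaves the number to be randomised undetermined.

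The replacement rule is also triggered by events after randomisation that the assignment can influence. The biofeedback arm asks for 12 in-person sessions; the control arm asks for 3 in-person and 3 online. Non-compliance and inability to attend are likely to arise differently under those two demands, so the rule may operate differently by arm. Nor does section 7.2 say whether attending control sessions counts as receiving the study intervention. If it does not, replacement is mandatory in one arm and optional in the other.

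Two outputs are at stake. One is the between-group estimate, which section 9.2 intends for powering a multi-center trial. The other is the clarity of Aim 2, where recruiting 40 and retaining them are themselves results.

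**Working it through.** **Step 1: the plan's own sample size.** Inputs from section 9.2, Table 4, peak knee extension moment: 3.7 (SD 0.9) and 2.4 (SD 0.5), two-sided alpha 0.05, power 80%.

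- Pooled SD = √((0.9² + 0.5²)/2) = √0.53 = 0.728.
- Standardised difference = 1.3/0.728 = 1.786.
- A two-sample t-test needs 6.05 per group, rounded up to 7, so 14 overall.

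This reproduces the stated 14. The other three rows of Table 4 also reproduce (5, 15 and 14 per group).

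**Step 2: the attrition allowance.** 30/40 = 75% retained, a 25% loss. Conversely, 30/(1 − 0.25) = 40. The figure of 40 is therefore 30 already inflated for the loss.

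**Step 3: add the section 7.2 rule at the same loss.** The documents do not say how far replacement goes, so two readings are shown. Both assume that every loss is a withdrawal that triggers replacement.

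- Each of the 10 losses replaced once: 40 + 10 = 50 randomised. Expected completers: 30 + 10 × 0.75 = 37.5.
- Replacement until 40 complete: 40/0.75 = 53.3, rounded up to 54.

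The documents give no other loss rate. An assumed range shows the sensitivity:

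| Assumed loss | Completers of 40, no replacement | Randomised, one replacement each | Randomised until 40 complete |
|---|---|---|---|
| 10% | 36 | 44 | 45 |
| 25% (section 9.2) | 30 | 50 | 54 |
| 30% | 28 | 52 | 58 |

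**Step 4: retention under section 9.4.3.** With all randomised in the denominator, 37.5/50 = 75% and 40/53.3 = 75%. Replacement does not change the figure.

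**Step 5: is replacement needed for power?** With 15 per arm (30 retained, evenly split), power is 0.997 for the knee extension moment and 0.826 for the weakest row of Table 4, the knee flexion angle. That row asks for 15 per group, and 2 × 15 = 30. The 30 retained therefore meet every row without replacement.

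**Step 6: where a shift towards completers would come from.** If everyone randomised is analysed, completers make up 75% with or without replacement. If the analysis keeps only completers, and a fraction q of an arm leaves with a mean change g SD worse, that arm's mean is too favourable by q × g. With q = 0.25 and g assumed between 0.5 and 1.0, this is 0.125 to 0.25 SD. The between-group difference is distorted to the extent that the two arms differ in q × g. The section 9.3 set does the selecting; replacement then refills that set with people who attend.

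**The case against.** The best defence is that replacement removes nobody. Section 7.2 does not say that replaced participants leave the dataset, section 7.1 says that stopping the intervention is not leaving the study, and section 5.5 encourages those who withdraw to complete assessments. All of this stands, and it confines the bias argument to the combination with section 9.3. It also means that deleting the replacement sentences without changing section 9.3 would leave the analysed set selected as before.

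A reader might infer several stronger points that the documents do not support:

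- **Retention would read 100%.** That needs replaced participants to drop out of the denominator. Section 9.4.3 divides by all randomised, which gives 75%.
- **Participants with an ACL tear disappear from view.** Withdrawal for a tear is at the investigator's discretion, adverse events are recorded whatever their cause (section 8.3.4), the safety set depends on visits attended and not on completion, and a tear is not the primary endpoint.
- **Allocation concealment is broken.** That assumes a replacement fills the vacated place. Section 6.3 has a computer-generated sequence held by the statistician, and a replacement could simply take the next assignment. The gap is that no rule is stated.
- **Recruitment would run to 32 months.** That (53.3 ÷ 40/24 per month) treats 40 in 24 months as the fastest possible pace. The protocol says only that it is confident of reaching 40 in that time.
- **40 is a fixed ceiling.** The documents speak of recruiting 40 and of a goal, which could be read as net of replacements. No passage says so, but this makes the sections unreconciled rather than numerically wrong.

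It is also fair that section 9.4.3 counts anyone who misses a biomechanical session as not retained. Withdrawals that trigger replacement may therefore be fewer than 10.

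**Conclusion.** The point holds as an unreconciled rule and should be fixed. Section 7.2 makes replacement mandatory after grounds that can depend on the arm, one of them worded for the biofeedback arm alone. Sections 4.1, 8.1 and 9.2 plan 40 with 10 losses already allowed for.

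Following both gives about 50 to 54 randomised, 10 to 14 above the stated number, with no cap and no allocation rule. The range rests on the 25% loss in section 9.2, on treating every loss as a withdrawal that triggers replacement, and on two readings of how far replacement goes.

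Replacement does not reduce power, delete data or alter the retention formula. The possible distortion of 0.125 to 0.25 SD in an arm's mean is illustrative, since the documents give no outcome difference between leavers and completers, and it depends on the section 9.3 set. The power figures apply to the proxy variables in Table 4, because section 9.2 has no earlier data on the symmetry index itself. For a pilot whose estimates will be carried forward, this is worth correcting but does not undermine the design.

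**What to change.** - **Section 7.2.** Replace the two replacement sentences with a statement that 40 participants will be randomised, that none will be replaced after randomisation, and that the section 9.2 allowance covers losses. People who consent but fail the baseline screen are not yet randomised, so new enrolments may still follow them.
- **Section 9.3.** Reconcile the modified ITT definition so that every randomised participant with outcome data is analysed in the assigned arm, whatever the attendance. An attendance-based set can remain as a sensitivity analysis.
- **Section 9.4.3.** Confirm in one sentence that all randomised participants stay in the Aim 2 denominator.

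The withdrawal grounds and participant care are not affected. The cost is a short protocol amendment and fewer completers than replacement would give: 30 at the planned loss, against 37.5 to 40. Those 30 are what section 9.2 plans on, more than twice the 14 that it says are needed.
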